2.0	1 Nov 2022	
 ● Added section about variations from original evaluation ● Updated number of FDAC sites and Local Authorities included in the study (Table 1) ● Updated Identification strategy section: changed severity of alcohol and drug misusing into type of misuse due to non-FDAC data availability ● Updated Outcome measure section: added an additional analysis of the number of different types of expert witness to deal with Research Question 5 ● Updated Matching section: updated Table 3 on matching variables; coarsening strategy for child, parent and case-level outcomes; and variables to be used by children-, parent- and case-level (details on changes can be tracked by comparing previous version of Table 3 “Intended variables for matching” in Appendix C) ● Updated Analysis plan section: changed model specification into a multilevel logistic regression to account for clustering effects; added a multilevel Poisson regression model to explore the difference between FDAC and non-FDAC cases in the number of different types of expert witness consulted during care proceedings. ● Updated Data source and availability section, in accordance with non-FDAC data availability ● Added new table listing misalignment between FDAC and non-FDAC data, along with derived variables to harmonise the data (Table 5) ● Updated Ethics & Participation section: regarding local authorities having to send out opt-out letters to parents receiving non-FDAC care proceeding ● Updated personnel list and timeline ● Expanded the date window for eligibility for study inclusion to maximise our sample size 
Minor changes:
 
 ● Used consistent terminology for child-, parent-, and case-levels of data ● Refer to the comparison group as non-FDAC care proceedings as usual, to match the language used with LAs ● Simplified the power analysis table to remove clusters with ICC = 0. (No change to calculation)

Table of contents

Table of contents	3
Background and Problem Statement	4
Children and Families Act 2014	4
The National Unit	4
Effectiveness	4
Variation between sites	5
Rationale for further evaluation of FDAC	5
Variations from original evaluation design	5
Intervention and Theory of Change	6
Impact Evaluation	8
Research questions	8
Participants	8
Design	9
Identification strategy	10
Data sources and availability	11
Minimum detectable effect size calculations	17
Outcome measures	18
Analysis plan	19

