FDAC case data will be retrieved directly from CJI following the development of a data sharing agreement. This data sharing agreement should be sufficient to enable access to all necessary FDAC data for the purposes of the study. Alternatively, however, separate data sharing agreements may have to be drawn for each of the individual FDAC sites. Further data sharing agreements will also be drawn for each of the participating Local Authorities in order to grant access to the necessary control case data.

Design

Table 2 Study design

² Note that this refers to RQ1, 2, 4 and 5. RQ3 draws on data from a prior cohort of FDAC participants (2017 and 2018).

³ Previously this was January 2021 – we expanded the date range to maximise sample size.

⁴ Manchester was the only Local Authority that agreed to provide non-FDAC care proceeding as usual data without an FDAC site in their area.

Study type and number of arms		Quasi-experimental design: Coarsened Exact Matching
Unit of identification		Case, parent, and child
Matching variables		Parent demographics, Domestic Violence, Alcohol or drug misuse, Child demographics, Case characteristics (see Table 3).
Primary outcome	variable	Reunification
	measure (instrument, scale)	Binary indicator derived from the placement of the child at the end of care proceedings.
Secondary outcomes	variables	
 1) Alcohol and drug misuse cessation; 2) Contested final hearing; and 3) Use of expert witnesses.
	measures (instrument, scale)	
 1) Binary indicator of whether the parent's alcohol and/or drug misuse has ceased; 2) Binary indicator of whether the final hearing was contested; 3) a) Binary indicator of whether expert witnesses were used during care proceedings; and b) Count of the number of different types of expert witness (based on the binary expert reports/assessments indicators, e.g. independent social work assessment, psychiatric assessment).

A randomised controlled trial was considered for this evaluation but was rejected as the judiciary thought that randomisation of families in care-proceedings could be subject to legal challenge. A feasibility study was conducted as part of this evaluation considering suitable evaluations. The impact evaluation, therefore, uses a quasi-experimental design: Coarsened Exact Matching (CEM).

Identification strategy

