The matching will be conducted using the user-written package *cem* in Stata 17.1 SE (Blackwell et al., 2010), which implements CEM as described in Iacus et al. (2009). The primary analysis will be conducted on an intention-to-treat basis where the outcome is non-missing. Where covariate data is missing, the *cem* package matches cases that are missing data on the same covariates. If missing outcome data exceeds five percent of the intervention sample, we will consider conducting a sensitivity analysis using multiple imputation (see missing data analysis).

Any intervention cases excluded from the analysis because no match can be found will be transparently reported using a CONSORT flow diagram. If more than five percent of intervention cases are lost because of issues with common support, we will consider adjusting how covariates are coarsened. This would involve collapsing categories of coarsened covariates and altering bin sizes. A summary of matching variables and how they will be coarsened can be found in Table 3.

Analysis

A “doubly robust” estimation of causal effects will be estimated for the matched sample, applying the weights assigned during the matching, including a binary indicator of allocation to FDAC, while also including the uncoarsened matching covariates in the regression model, following Funk et al. (2011). The “doubly robust” estimation reduces the risk that the average treatment effect on the treated (ATT) is biased, provided that either the matching (modelling exposure to the intervention) or the regression model (describing the relationship between the dependent and independent variables) is well specified (Funk et al., 2011). To account for the clustering of children within primary carers, cases and within sites (as shown in Table 1)⁸, we will use a multilevel logistic regression model. The full model is as follows:

$$P(\text{Reunification}_{ipcs}) = \text{logit}^{-1}(\beta_0 + \beta_1 \text{Intervention}_{ipcs} + \beta_2 X_{ipcs} + u_{pcs} + u_{cs} + u_s)$$

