Where $P(\text{Reunification}_{ipcs})$ is the probability of reunification. Children (i) are nested within primary carers (p), cases (c), and sites (s). The vector X_{ipcs} denotes the uncoarsened covariates. The random intercepts are represented as u_{pcs} , u_{cs} , u_s , respectively. Should the random intercept adjustments at primary-carer-level and case-level be significantly highly correlated (over .8) with each other, we will drop case-level random intercepts from the model.

The multilevel models described above will be estimated using the *melogit* command in Stata.

Additional Analysis

As a sensitivity analysis, we will fit a multilevel logistic regression model on the matched sample excluding the characteristics used in the matching in the regression model:

$$P(\text{Reunification}_{ipcs}) = \text{logit}^{-1}(\beta_0 + \beta_1 \text{Intervention}_{ipcs} + u_{pcs} + u_{cs} + u_s)$$

Secondly, we will also assess the impact of FDAC on the placement of the child (RQ6), using a categorical outcome variable that indicates 1) reunification with the child’s parents 2) placement with another relative, or 3) LA care. This will be assessed using a multilevel multinomial logistic regression.

$$P(\text{Placement}_{ipcs}) = \text{logit}^{-1}(\beta_0 + \beta_1 \text{Intervention}_{ipcs} + \beta_2 X_{ipcs} + u_{pcs} + u_{cs} + u_s)$$

As with the primary analysis, we include the uncoarsened covariates used in matching. We will present effect sizes as relative risk ratios, with 95% confidence intervals. The risk ratio will be estimated as described above.

Missing data analysis

⁸ Site refers to case locations, as shown in Table 1. Control cases will be coded as the FDAC site that serves their Local Authority (e.g. both Coventry and Warwickshire non-FDAC data will be allocated to Coventry site data). Manchester will be coded independently as there is no FDAC site.

If greater than five percent of cases are missing outcome data on the primary analysis, it is likely that missingness may impact the results of the evaluation and we will therefore consider conducting additional analysis for the primary outcome.

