Further ethical clearance will be requested from NatCen's ethics committee for the IPE in December 2020, when plans and timings for fieldwork, (including the selection of case study areas) have been agreed. We will also seek ethical approval from the judiciary in order to conduct interviews with judges and magistrates for the IPE. Once case study areas have been decided, applications will be submitted to the relevant Head of Division or the Senior Presiding Judge, as stipulated in the Courts and Tribunals Judiciary guidance.¹³ We are experienced in seeking ethical approval to carry out research with members of the judiciary, which will help us to prepare applications and requests for these approvals.

Ethical clearance was revisited in July 2022, confirming an ethical requirement to notify parents whose case was seen by non-FDAC care proceedings as usual of the use of their data with a requirement to provide an option for them to opt-out. NatCen and WWCS researchers consulted with each other and all parties agreed to send a letter to parents informing them of the use of their data and the reasons for the use of their data within this project giving the parents and their children the right to opt-out of their data being used within a reasonable timeframe. Local Authorities are expected to send out an opt-out letter to data subjects in August 2022, unless exemptions apply.

Registration

The study has been pre-registered on the Open Science Framework on December 4th, 2020. The registration can be found here: <https://osf.io/w7zac>.

Data protection

NatCen will be the data controller for the duration of the impact evaluation and will be responsible for the collection, processing and storage of the data. NatCen has signed data sharing agreements with Local Authorities for sharing non-FDAC care proceedings data, with FDAC sites for sharing data from FDAC cases and with WWCS for sharing personal data.

The legal basis for processing and sharing the data under GDPR Article 6 1(f) is 'legitimate interests', with processing of special categories of personal data for scientific research purposes under GDPR Article 9 2(j). This means that there is a good reason for NatCen to collect and manage this data, and that this data is needed to evaluate and learn about FDACs.

¹³ <https://www.judiciary.uk/publications/judicial-participation-in-research-projects/>

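### A data opt-out is described only for control families, at a time when most would know their outcome, and the plan neither counts opt-outs explicitly nor tests what they could do to the primary risk ratio

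*Supplement*

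**What the plan says.** Ethics & Participation in protocol version 2.0 reports that ethical clearance was revisited in July 2022 and confirmed "an ethical requirement to notify parents whose case was seen by non-FDAC care proceedings as usual of the use of their data". The agreed letter is described as "giving the parents and their children the right to opt-out of their data being used within a reasonable timeframe". On timing: "Local Authorities are expected to send out an opt-out letter to data subjects in August 2022, unless exemptions apply". The version history lists the change as "regarding local authorities having to send out opt-out letters to parents receiving non-FDAC care proceeding". Both places name non-FDAC parents only.

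For the intervention arm, the Participants section says "FDAC case data will be retrieved directly from CJI following the development of a data sharing agreement", with site-level agreements as the alternative. No opt-out step is attached to that route.

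The Matching part of the primary analysis defines the analysis set: "The primary analysis will be conducted on an intention-to-treat basis where the outcome is non-missing". Missing data analysis begins "If greater than five percent of cases are missing outcome data on the primary analysis" and goes on to a drop-out model on the matching covariates and, if that model finds associations, multiple imputation. The Identification strategy promises a CONSORT flow diagram of losses and exclusions but does not mention opt-outs.

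**The concern.** A right to withdraw that operates in one arm, after the outcome is known, can select that arm on the outcome. The primary outcome is where the child lives when proceedings end. A parent who receives the letter after the final hearing knows the result, and the letter comes from the authority whose concerns underlay the case. A link between opting out and the result is plausible in either direction.

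The control reunification rate is the denominator of the primary risk ratio. If parents whose children did not come home opt out more often, the observed control rate rises and FDAC looks less effective. If parents whose children did come home opt out more often, it falls and FDAC looks more effective. The Participants section concedes selection into FDAC, but not this second selection, which happens after the outcome.

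**Working it through.** **The plan's own target.** Inputs from Minimum detectable effect size calculations and Table 5: control rate 25%, ICC 0.70, R-squared 0.20 (child) and 0.10 (parent), 600 children in 430 cases, two-sided alpha 0.05, power 0.80. Using the Appendix F approach, with the 0.10 applied to the ICC term and the odds-ratio conversion read as an exponential:

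- MDES = 2.808 × √[0.70 × 0.90/(0.25 × 430) + 0.30 × 0.80/(0.25 × 600)] = 0.243
- OR = exp(0.243 × π/√3) = 1.55
- RRR = 1.553/(0.75 + 0.25 × 1.553) = 1.364, or 9.1 points

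This matches the stated 1.36 and 9.1 points. The FDAC rate at the target is therefore 34.1%.

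**How many cases would have ended when the letter was due.** Participants gives the window: open October 2019 to June 2022, final hearing by October 2022. Assume even issue dates and a fixed duration of D months. Count months from 1 October 2019, so that 1 August 2022 is month 34 and the end of October 2022 is month 37. For cases issued within the window, the share ended by 1 August is (34 − D)/(37 − D):

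- D = 6 (the 26 weeks given as typical): 28/31 = 90%
- D = 9: 25/28 = 89%
- D = 12: 22/25 = 88%

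Counting cases already open in October 2019 gives 34/37 = 92%. So roughly 88% to 92% under these assumptions.

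**What the planned safeguards can see.**

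| Safeguard | Acts on | Corrects outcome-related opt-out? |
|---|---|---|
| CEM weights, balance checks | Baseline variables of held records | No |
| Covariates in the regression | Baseline variables of held records | No, for selection on outcome within covariate levels |
| Five per cent trigger, drop-out model, imputation | Held records with the outcome missing | No, if the record is not used at all |
| CONSORT diagram | Losses that are reported | Could show a count, not a link with outcome |

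**Possible size.** The documents give no opt-out rate, so these are assumptions. Let o be the share of control children opted out, and k the risk of opting out in non-reunified relative to reunified families.

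- Opt-out risk if reunified: a = o/(0.25 + 0.75k)
- Observed control rate = 0.25(1 − a)/(1 − o)
- Apparent RR = FDAC rate / observed control rate

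Example, o = 10% and k = 3: a = 0.10/2.5 = 0.04; observed rate = 0.25 × 0.96/0.90 = 26.7%; RR = 0.341/0.267 = 1.28.

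Example, o = 10% and k = 1/3: a = 0.10/0.5 = 0.20; observed rate = 0.25 × 0.80/0.90 = 22.2%; RR = 0.341/0.222 = 1.53.

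| o | k | Observed control rate | True 1.36 appears as | True null appears as |
|---|---|---|---|---|
| 5% | 3 | 25.8% | 1.32 | 0.97 |
| 10% | 3 | 26.7% | 1.28 | 0.94 |
| 20% | 3 | 28.8% | 1.19 | 0.87 |
| any | 1 | 25.0% | 1.36 | 1.00 |
| 5% | 1/3 | 23.7% | 1.44 | 1.06 |
| 10% | 1/3 | 22.2% | 1.53 | 1.13 |
| 20% | 1/3 | 18.8% | 1.82 | 1.33 |

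The two directions are not symmetric. Reunified children are the smaller group, so their selective loss moves the rate further. At o = 20% and k = 1/3, 40% of reunified controls would have to be opted out, which is an extreme case.

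**Worst-case bounds**, for an observed control rate of 25% and FDAC at 34.1%: the true control rate lies between 0.25(1 − o) and 0.25(1 − o) + o. With o = 10% that is 22.5% to 32.5%, so the RR lies between 0.341/0.325 = 1.05 and 0.341/0.225 = 1.52.

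**The case against.** Several stronger readings are tempting, and the documents do not support them.

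- *FDAC parents have no right to withdraw.* A reader might infer this, but it is an argument from silence. Both places that describe the letter name non-FDAC parents only, and nothing says FDAC parents received no notice or choice. Part of the text following Data protection was also removed from the copy reviewed. What stands is that no equivalent is described.
- *Opted-out families are never sent to the evaluator, so nothing in the plan could register them.* The protocol does not say whether records are withheld or deleted after supply, or whether a count is kept. The flow diagram of losses could carry that count. Either way, a family that has refused use of its data cannot feed the drop-out model or the imputation, and a count does not reveal a link with outcome.
- *Some authorities send no letter at all.* The exemption wording follows a reference to individual data subjects and may concern individuals. Nothing can be built on a contrast between authorities.
- *The estimate is biased by a known amount.* Rates and direction are both assumed. The figures are also crude: matching and covariate adjustment would absorb any part of opting out explained by baseline variables.

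It is also fair to say that the opt-out is an ethical requirement and not a free design choice, and that Local Authorities had already asked for a lighter data burden. Neither point prevents the loss from being counted and its possible effect bounded.

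**Conclusion.** The point holds as a cheap improvement. As described, the plan gives one arm an exit that most families would reach after learning the outcome, and it has no analysis able to correct the resulting loss. It does not show that bias exists.

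Under assumed opt-out of 5% to 20% with a threefold difference by outcome, the apparent risk ratio falls by 3% to 13% if non-reunified controls leave more, and rises by 6% to 33% if reunified controls leave more. The control rate moves by 0.8 to 6.3 percentage points, against a detectable difference of 9.1. If opting out is rare or unrelated to outcome, the effect is negligible or nil.

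The conclusion rests on three things: the letter going only to control families, as the text describes it; even issue dates with proceedings of 6 to 12 months; and a 25% control rate. Opt-out counts would show which part of the range matters.

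**What to change.** 1. Ask each participating Local Authority for anonymous totals: eligible control children and cases identified, letters sent, exemptions applied, and children and cases opted out.
2. Name opt-outs in the flow diagram as a control-arm loss. State whether FDAC families had any comparable choice and, if so, show the same count for them.
3. Pre-specify a bounding or tipping-point sensitivity analysis of the primary RRR. Vary the relative risk of opting out (non-reunified versus reunified) from 1/3 to 3 at the observed opt-out share, and report the worst-case bounds beside it.

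The analysis should not depend on the outcomes of families who refused use of their data, and it should not compare authorities that sent letters with any that were exempt.

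Cost: a few summary numbers from each of 12 Local Authorities and one sensitivity analysis, with no personal data on opted-out families. Version 2.0 is dated 1 November 2022, after the letters were due, so the counts should exist. The downsides are a small extra request to authorities already short of resources, possible suppression of small numbers, and a less certain headline estimate if opting out proves common.

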Appendix A – FDAC Logic Model

INPUTS	ACTIVITIES	OUTPUTS	INTERIM OUTCOMES	Long term outcomes	

FDAC team
 
Budget for the team including:
 
 Salaries and on costs Non staff costs Training Travel Testing Equipment and accommodation 	
Strategic activity
 
 Engagement with commissioners Engagement with treatment services Engagement with children services Communications materials 	
 Budget and commissioning systems agreed Local leaflets and other materials regularly disseminated Minimum of 2 lawyers and Guardian forums every year FDAC team link for treatment services, quarterly meetings Quarterly Steering groups held Quarterly Operational groups held FDAC Team including Judges, where possible, to attend training with NU every 4 months FDAC team hold in house training days every 6 months, such as VIG or testing 	
Professionals Knowledge/awareness/Buy in
 
 More Key stakeholders have awareness that FDAC is up and running More Key stakeholders understand the model (problem solving approach to care proceedings) More champions for the model in local authority senior management and in the judiciary More stakeholders are convinced of the benefits of the FDAC approach Commissioner are convinced that FDAC should have ongoing funding 		
Proportion of children living with the same primary carer with whom they were living before the start of proceedings, at the end of proceedings


Judicial and court time
 
 Judges time Court staff and administration times Listing office time 	
Operational activity
 
 FDAC Team attendance at court Pre-court meetings Day assessment with each family in 1st week of proceedings. Team organise IPMs and and chair review IPMS, and file minutes Team write initial parenting report, review reports and review parenting assessment report, minutes of meetings and circulate to all parties and court. The FDAC team hold regular key work, using MI and other interventions. The FDAC team chair Children's Needs meeting within first 10 weeks, and file minutes. Recruit, train and supervise parent mentors Organise and ensure team attendance at reflective supervision Drug treatment and testing Child psychiatry 	
 All parents met at court for first hearing by FDAC team All parents meet their allocated FDAC Judge and continue to meet same Judge throughout proceedings All parents have initial assessment by multi-disciplinary team within first 4 weeks FDAC team will formulate each case as a multidisciplinary team. All parents have an Intervention planning meeting within 4 weeks, and attended by FDAC team, parents, children's services, Guardian and treatment providers where possible. Initial Parenting assessment report and intervention plan presented to Court for 2nd Hearing. Once parents signed up to FDAC, parents proceed with regular fortnightly Non-Lawyer reviews Continuous monitoring and support by a therapeutic team, including regular testing, keywork and review reports. All parents will have a review IPM held at 10 weeks and 18 weeks. All parents will have been offered interventions delivered by local services and the FDAC team matched to their needs. All parents have a review parenting assessment report filed with Court for the IRH, which will include final recommendations, and options for post proceedings support. All parents will have had a time-limited highly coordinated therapeutic 'trial for change' by the end of proceedings Parent mentors will be present at Court and all parents will be offered option of support from a parent mentor. Team attend reflective supervision every 8 weeks Team and Judges will have attended initial and follow up training on a regular basis Team and Judges will be mindful of timescales and the National requirements Problem solving court approach is embedded in local court Parties recognise expertise of FDAC team 	
Parents' outcomes in FDAC as opposed to normal proceedings
 
 More engagement of parents in the court processes and with treatment and other services More parents are able to cease misusing substances and sustain their recovery More parents are able to resume care of their children More parents show improvement in their mental health More parents and children are protected from the impact of domestic abuse More improved relationships between parents and children even when children are not going to return home More parents have insight into why they have not been reunited with their children 		
Proportion of parents who have ceased substance misuse at end of proceedings


LA and other agency time
 
 Senior Mgt time for Social worker's time Guardian's time Treatment provider's time Mentors – Budget, recruitment and support 	
Training and development
 
 Attending training Organising in service training days 		
Court outcomes
 
 The team and judges are more skilled at working in line with the problem solving approach within timescales appropriate for children in care proceedings Proceedings when children do not go home will end within the National and Local requirements around 26 weeks More proceedings will end without a final contested hearing More proceedings do not require any other externally funded experts, other than FDAC More proceedings take place without a residential placement for similar type of cases 		
Proportion of FDAC than comparison reunification parents with sustained cessation over the follow up period

				
A proportion of FDAC than comparison reunifications parents who experienced no disruption to family stability over follow up period
	
				
Procedural fairness experience
	

